9.11 End of Treatment and Study Drug Discontinuation

9.11.1 End of Treatment

Patients may voluntarily withdraw from the study or be dropped from it at the discretion of the investigator at any time. In addition, the investigator should discontinue study drug if he or she thinks that continuation would be detrimental to the patient's well-being.

If such withdrawal occurs, or if the patient fails to return for visits, the investigator must determine the primary reason for a patient's premature withdrawal from the study and record the information on the electronic Case Report Form (eCRF). If the reason for withdrawal is an AE, monitoring will continue until the outcome is evident. The specific event or test result(s) must be recorded in the eCRF.

Patients may be withdrawn from the study prematurely for one of the following reasons:

- Adverse event(s)
- Abnormal laboratory value(s)
- Abnormal test procedure result(s)
- Protocol violation
- Subject withdrawal of consent
- Loss to follow-up
- Administrative problems
- New cancer therapy
- Disease progression
- Death
- Withdrawal of a patient at the specific request of the sponsor.

The sponsor must be notified within 24 hours if a patient is withdrawn from the study.

Patients who withdraw or discontinue before having received study drug on Cycle 2 Day 22 will only be replaced if the reason for withdrawal/discontinuation was not lack of efficacy.

Patients will not be replaced after they have received treatment for Cycle 2 Day 22, regardless of the reason of withdrawal or discontinuation.

Patients who are withdrawn for any reason may not re-enter this clinical study at any time.

9.11.2 Study Drug Discontinuation

Study drug must be discontinued for a given patient if the investigator determines that continuing it would result in a significant safety risk for the patient.

Patients who discontinue study before completing the second cycle and response assessment should be scheduled for a visit as soon as possible, at which time all of the assessments listed for the End of Study visit should be performed. At a minimum, all patients who discontinue study treatment, including those who refuse to return for a final visit, will be contacted for safety evaluations during the first 4 weeks following the last dose of study drug.

Patients who discontinue study drug should be considered withdrawn from the study after the final visit assessments are performed or when it becomes clear that the patient will not return for these assessments. The last day of study drug administration should be entered into the eCRF and the reason for discontinuing study drug should be given. Patients lost to follow-up should be recorded as such in the eCRF. Treatment after study drug discontinuation is at the discretion of the investigator.

9.12 Study or Site Termination

The investigator and the sponsor both reserve the right to terminate the study at any time at a given clinical study center. The sponsor also reserves the right to terminate the entire study or temporarily interrupt enrolment and/or dosing of already enrolled patients for further evaluation, eg, if during ongoing evaluation of the risk/benefit ratio the sponsor decides that the risks outweigh the benefits of MOR00208.

Stopping criteria for this study will include, but not be limited to:

1. Two or more patients within the first six patients enrolled experience unexpected Grade 4 or 5 toxicities of the same or related Adverse Event terms according to CTC and these events are assessed as being related to MOR00208 by the investigator or the sponsor.
2. $\geq 30\%$ of patients following the initial six enrolled experience unexpected Grade 4 or 5 toxicities of the same or related Adverse Event terms according to CTC and these events are assessed as being related to MOR00208 by the investigator or the sponsor.

Should a termination of a given clinical study center or the whole study be necessary then the procedures will be arranged on an individual study basis after review and consultation by all involved parties. In terminating the study, the sponsor and the investigator will ensure that adequate consideration is given to the protection of the patients' interests. Institutional Review Boards (IRBs)/IECs and competent authorities will be notified of premature termination in accordance with applicable regulatory requirements.

10 VISIT SCHEDULE AND ASSESSMENTS

[Table 2](#) lists all of the assessments, and indicates with an "X" the visits at which these assessments are performed. All data obtained from these assessments must be supported in the patient's source documentation.

Table 2 Schedule of Assessments

Evaluation or Procedure	Screening	Cycle 1 (28 days)					Cycle 2 (28 days)					Cycle 3 (if response is at least SD) (2 weeks ± 1 day after Cycle 2 Day 22)					Follow-up		Maintenance Treatment Visits beyond Follow-up Visit 12 ²⁰	EOS Visit	
		-21 to -1	Day 1	Day 2	8 ± 1 day	15 ± 1 day	22 ± 1 day	1 ± 1 day	8 ± 1 day	15 ± 1 day	22 ± 1 day	28 ± 4 days	1 ± 1 day	8 ± 1 day	15 ± 1 day	22 ± 1 day	28 ± 4 days	1 st Follow-up + 4 weeks ± 2 days			Follow-up Visits 2 - 12 ¹
Informed consent	X																				
Inclusion/exclusion criteria	X	X ²																			
Demography	X																				
Medical history (incl. prior NHL treatments)	X																				
Staging	X																				
ECOG	X	X			X		X		X				X		X			X	X		X
Determination of CD19 on tumor cells (bone marrow)	X																				
Determination of CD19 on tumor cells (tumor biopsy/aspirate) ³	X																				
Study drug administration		X		X	X	X	X	X	X	X		X	X	X	X					X ²⁰	
Premedication		X		X	X	X ⁴	X ⁴	X ⁴	X ⁴	X ⁴		X ⁴	X ⁴	X ⁴	X ⁴						
“Emergency laboratory”		X ¹⁹		X ¹⁹	X ¹⁹	X ¹⁹	X ¹⁹	X ¹⁹	X ¹⁹	X ¹⁹		X ¹⁹	X ¹⁹	X ¹⁹	X ¹⁹						
Haematology	X	X ²	X	X ²	X ²	X ²	X ²	X ²	X ²	X ²	X	X ²	X ²	X ²	X ²	X	X	X	X	X	X
Serum chemistry	X	X ²	X	X ²	X ²	X ²	X ²	X ²	X ²	X ²	X	X ²	X ²	X ²	X ²	X	X	X	X	X	X
Coagulation	X	X ²					X ²					X ²					X	X	X		X
Pharmacokinetics		X ⁵		X ⁶	X ⁶	X ⁶		X ⁶		X ⁶	X		X ⁶		X ⁶	X	X	X ⁷			
Urinalysis	X	X ²					X ²					X ²					X	X			X
β-HCG pregnancy test (WOCBP)	X																X ²²	X ²²			X
Urine pregnancy test (WOCBP)		X ²					X ²					X ²					X ²²	X ²²	X		
Serology (Hepatitis B and C)	X					X ²¹					X ²¹					X ²¹	X ²¹	X ²¹	X ²¹		
B-, T- and NK cell flow cytometry		X ²		X ²	X ²	X ²		X ²		X	X ²		X ²		X						X
CD16 expression on NK cells	X						X ²					X ²					X	X ¹⁸			
Anti-MOR00208 antibodies		X ²					X ²					X ²									
FcγR polymorphism (mucosal cheek swab)		X ²																			

Table 2 Schedule of Assessments

Evaluation or Procedure	Screening	Cycle 1 (28 days)					Cycle 2 (28 days)					Cycle 3 (if response is at least SD) (2 weeks ± 1 day after Cycle 2 Day 22)					Follow-up		Maintenance Treatment Visits beyond Follow-up Visit 12 ²⁰	EOS Visit + 4 weeks ± 2 days	
		-21 to -1	Day 1	Day 2	8 ± 1 day	15 ± 1 day	22 ± 1 day	1 ± 1 day	8 ± 1 day	15 ± 1 day	22 ± 1 day	28 ± 4 days	1 ± 1 day	8 ± 1 day	15 ± 1 day	22 ± 1 day	28 ± 4 days	1 st Follow-up + 4 weeks ± 2 days			Follow-up Visits 2 - 12 ¹
ADCC assessment	X																				
Tumor biopsy (cytogenetics) ³	X																				
Serum immunoglobulin levels		X ²				X ²				X ²					X ²		X	X		X	
Bone marrow aspiration & biopsy	X ⁹										X					X ¹⁰		X ^{10, 8}			
Body weight	X	X		X	X	X	X	X	X	X	X	X	X	X	X	X	X	X	X	X	X
Physical examination	X ¹¹	X ²				X					X ¹²					X ¹²	X ¹²	X ¹²	X	X	
Vital signs	X	X ¹³	X	X ¹³	X ¹³	X ¹³	X ¹³	X ¹³	X ¹³	X ¹³	X	X ¹³	X ¹³	X ¹³	X ¹³	X	X	X	X	X	
ECG	X	X ¹⁴						X ¹⁴	X ¹⁴	X ¹⁴					X ¹⁴					X	
AE assessment											-----continuous-----										
Baseline disease and response assessment (CT/PET) ¹⁵		X ^{2, 17}									X ¹⁷					X ¹⁷		X ^{8, 17}			
Additional Radiological evaluation ¹⁶		X ¹⁷									X ¹⁷					X ¹⁷		X ^{8, 17}			
Previous/Concomitant medication	X	X	X	X	X	X	X	X	X	X	X	X	X	X	X	X		X	X	X	

Abbreviations: ADCC = antibody-dependent cell-mediated cytotoxicity; AE = adverse event; β -HCG = beta-human chorionic gonadotropin; C2D22 = Cycle 2 Day 22; CT = computed tomography; ECG = electrocardiogram; ECOG = Eastern Cooperative Oncology Group; EOS = End of Study; FU= Follow-up; PET = positron emission tomography; SD = stable disease; WOCBP = woman of childbearing potential.

¹ The second and third FU Visit should be scheduled 6 weeks \pm 1 weeks following the previous visit, the fourth to sixth FU Visit should be scheduled 3 months \pm 2 weeks following the previous visit, further FU Visits should then be scheduled every 6 months.

² Before study drug administration.

³ Tumor biopsy/aspirates should be obtained if malignant lymph nodes are easily accessible.

⁴ Premedication for patients who do not experience infusion reactions during the first 3 infusions will be optional at the discretion of the investigator for subsequent infusions.

⁵ The PK sample will be taken before study drug administration; at the end of the infusion; and 1 hour, 4 hours, and 24 hours after end of first MOR00208 infusion. The sample taken on Day 2 (ie, 24 hours after end of first infusion) belongs formally to Day 1.

⁶ The PK sample will be taken before study drug administration and 1 hour after the end of MOR00208 infusion.

⁷ The PK sample will be taken at second and third follow-up visit only.

⁸ Not performed at third FU (no response assessment).

⁹ Results from bone marrow examination done within 4 weeks before screening are acceptable, if the patient's disease has been stable since then. In this case, obtaining bone marrow samples for the sole purpose of CD19 expression does not need to be repeated.

¹⁰ Bone marrow examinations should only be repeated if response at last bone marrow examination was not CR.

¹¹ Including body height at screening only. Physical examination includes palpable tumor assessment, general appearance, skin, head, eyes, ears, nose, throat, lungs, breasts and axillae (if applicable including bi-dimensional measurement of cervical, supraclavicular, axillary and inguinal lymph nodes), cardiovascular system, back and spine, abdomen (if applicable including spleen size below the costal margin), extremities, infusion site, lymph nodes, and neurological examination.

¹² Physical examination will be used for response assessment.

¹³ Immediately before infusion; 15, 30, and 60 minutes during infusion; at end of infusion; and every hour for two hours after completion of infusion.

¹⁴ Performed 1 hour \pm 10 minutes post dose. Additionally, for Cycle 1 Day 1 predose; 12-lead ECG recording should include determination of heart rate and RR, PR, QRS, QT, and QTc intervals. The 12-lead ECG will be recorded after 5 minutes of rest in a supine position.

¹⁵ For all patients neck/chest/abdomen/pelvis CT is required. PET should also be performed for response assessment if tumor was PET avid at baseline.

¹⁶ Radiographic examinations in addition to the neck/chest/abdomen/pelvis CT/PET evaluations are to be done, as appropriate. (For MRI, please see Section 10.6.) Follow-up radiographic examinations will be performed at the end of Cycle 2, Cycle 3, and at the second and subsequent follow-up visits for any procedures performed at baseline visit.

¹⁷ Radiographic evaluations may be performed up to 3 days before the scheduled visit during Cycle 1-3 and within +/- 4 days of the planned visit during follow-up. If a patient discontinues from the study before a response assessment, an evaluation will occur approximately one month after the patient discontinues from the study. CT/PET examinations that were done up to 3 weeks before Cycle 1 Day 1 may be used as a patient's baseline assessment. (For MRI, please see Section 10.6.)

¹⁸ Anti-MOR00208 sample will be taken at third follow-up visit only.

¹⁹ Sample to be taken and evaluated before study drug administration.

²⁰ Maintenance treatment for patients with at least ongoing PR will be administered either every second week or monthly until progression. The treatment frequency during the follow up period should be maintained. Before administration, blood parameters (hematology, serum chemistry, urine pregnancy test) should be evaluated in local laboratory according to local guidelines/practice for the administration of monoclonal antibodies. Vital signs should be measured every hour or according to local practice with anti-CD20 antibodies.

²¹ Hepatitis C serology only to be done at screening. HBV-DNA only to be measured during treatment and follow-up if total anti-HBc was positive. If HBV-DNA is positive, please see Section 9.5.2. Anti-HBc should be measured if an anti-HBc status from during the study or within 6 months prior to screening is not known.

²² Only urine pregnancy test is to be done if the regular follow-up visit coincides with the maintenance treatment visit. Otherwise, serum pregnancy test should be done.

10.1 Screening Evaluations

All patients must have signed and dated the informed consent before initiation of any study-related evaluation. However, assessments that have been performed before the signing of the informed consent and that fall within the screening period window may be used as screening assessments **only if** the assessments were performed as part of the routine standard of care visit for the patient. The investigational site must provide a note to file in the patient folder to attest to any such occurrence. The screening period lasts for up to 21 days. All patients must satisfy all of the inclusion criteria and none of the exclusion criteria listed in Sections 8.1 and 8.2.

The screening evaluations will include:

- Demography and ECOG performance status (see the appendix, Section 17.5)
- Prior and concomitant medication
- Medical history and physical examination including height, weight, palpable tumor assessment, general appearance, skin, head, eyes, ears, nose, throat, lungs, breasts and axillae (if applicable including bi-dimensional measurement of cervical, supraclavicular, axillary and inguinal lymph nodes), cardiovascular system, back and spine, abdomen (if applicable including spleen size below costal margin), extremities, infusion site, lymph nodes, and basic neurological examination)
- Staging
- Blood sampling:
 - Haematology with complete blood count (CBC) with differential and platelet count, serum chemistry, and coagulation
 - β -HCG pregnancy test for women of childbearing potential
 - Determination of CD16 expression on NK cells and ADCC assessment (Due to the exploratory nature of the ADCC assay, the sponsor may decide at any point during the study to terminate these assessments in which case the sites will be informed accordingly)
 - Hepatitis B and C screening (please see Section 9.5.2)
- Urine sampling for urinalysis
- Bone marrow aspirate and biopsy. Results from bone marrow examination done within 4 weeks before screening are acceptable, if the patient's disease has been stable since then. The following are included:
 - Histology (to be analysed locally)
 - Determination of CD19 on malignant B cells (to be done through central lab)
- Tumor aspirate and biopsy, if malignant lymph nodes are easily accessible. The following are included:
 - Histology (to be analysed locally)
 - Determination of CD19 on B cells (to be analysed through central lab)

- Cytogenetics (if historical data are not available, to be analysed locally)
- Vital signs (pulse, blood pressure, temperature and respiratory rate)
- 12-lead ECG

10.2 Main Treatment Phase (Cycles 1-3)

Only patients fulfilling all inclusion and none of the exclusion criteria should be enrolled.

The schedule of required procedures for each treatment day is detailed in [Table 2](#). Clinical site study days are Days 1, 2, 8, 15, and 22 for Cycle 1 and Days 1, 8, 15, 22, and 28 for Cycle 2. Patients qualifying for Cycle 3 will have visits on Days 1, 8, 15, 22, and 28 of this cycle.

During the first two 28-day cycles, patients will receive a total of 8 infusions: each 28-day cycle will consist of a MOR00208 infusion on Day 1, Day 8, Day 15 and Day 22 of the cycle.

- Patients with a response of at least SD on Cycle 2, Day 28, will qualify for 1 further cycle of MOR00208 (infusions on Day 1, Day 8, Day 15 and Day 22 of the 28-day cycle). This potential Cycle 3 should start 2 weeks \pm 1 day after Cycle 2, Day 22.

Before dosing, premedication as detailed in [Section 9.5](#) should be administered.

Clinical assessments, physical examinations and laboratory evaluations (instead of emergency lab) may be performed within 24 hours before administration of MOR00208 (except PK and anti-MOR00208 antibodies); assessments for Cycle 3 should only be performed if patient qualifies for the respective study drug administration:

- Assessment of AEs and concomitant medication at all visit days (see [Section 9.8](#))
- Assessment of body weight at all visit days
- Physical examination including palpable tumor assessment, general appearance, skin, head, eyes, ears, nose, throat, lungs, breasts and axillae (if applicable including bi-dimensional measurement of cervical, supraclavicular, axillary and inguinal lymph nodes), cardiovascular system, back and spine, abdomen (if applicable including spleen size below the costal margin), extremities, infusion site, lymph nodes and neurological examination at Day 1 (predose) and Day 22 of Cycle 1; and Day 28 of Cycles 2 and 3.
- ECOG performance status (Day 1 and 15 of Cycles 1 to 3)
- Vital signs (pulse, blood pressure, temperature and respiratory rate): At each treatment visit immediately before infusion, 15, 30, 60 minutes (\pm 5 minutes) after start of infusion, at the end of the infusion, and every hour for two hours (\pm 10 minutes) after completion of the infusion. If the infusion is interrupted and/or subsequently restarted, vital signs should be assessed every 60 minutes after the first hour until two hours after the end of the infusion. Vital signs should be obtained once on Day 2 Cycle 1 and on Day 28 of Cycles 2 and 3.

- Baseline disease status on Day 1 of Cycle 1 and response assessment on Day 28 of Cycles 2 and 3 should include:
 - Assessment by physical examination
 - CT of neck, chest, abdomen and pelvis on Day 1 of Cycle 1 and Day 28 of Cycles 2 and 3 (for MRI, please see Section 10.6). A PET scan should also be used for response assessment if CT does not provide a clear readout and if the lymphoma is expected to be PET-avid. Results from CT and/or PET examination done within 3 weeks before Cycle 1 Day 1 are acceptable to be used for baseline. Radiographic examinations can be done up to 3 days before the treatment visit.
 - Radiological evaluation in addition to the CT/PET of neck, chest, abdomen and pelvis are to be done as appropriate on Day 1 of Cycle 1 and Day 28 of Cycles 2 and 3 (for MRI, please see Section 10.6). Results from additional radiological evaluations done within 3 weeks before Cycle 1 Day 1 are acceptable to be used for baseline. Radiographic examinations may be performed up to 3 days before the treatment visit.
 - Bone marrow aspiration and biopsy (baseline assessment should be done during screening and not on Day 1 of Cycle 1).
- Laboratory assessments from blood sampling (Day 1 preinfusion assessments will be considered baseline assessments):
 - Blood sample for “emergency laboratory” for immediate evaluation before study drug administration on all Days 1, 8, 15, 22 of Cycles 1, 2 and 3 (if Cycle 3 is applicable) if no blood sample from the 24 hours before study drug administration is available.
 - Haematology including CBC with differential and platelet count and serum chemistry before each infusion of MOR00208 and on Day 2 of Cycle 1 and Day 28 of Cycles 2 and 3.
 - Coagulation before infusion on Day 1 of Cycles 1 to 3
 - PK samples:
 - Cycle 1, Day 1 : before infusion, at the end of infusion (\pm 10 minutes) and 1 hour (\pm 10 minutes), 4 hours (\pm 10 minutes) and 24 hours (\pm 1 hour) after end of first MOR00208 infusion
 - Cycle 1, Days 8, 15 and 22; Cycles 2 and 3, Days 8 and 22: before infusion and 1 hour after the end of infusion (\pm 10 minutes)
 - Cycles 2 and 3, Day 28
 - B-, T- and NK cell flow cytometry before infusion on Days 1, 8, 15 and 22 of Cycle 1 and on Days 1, 15 and 28 of Cycles 2 and 3.
 - Anti-MOR00208 antibodies before infusion on Day 1 of Cycles 1 to 3.
 - Serum immunoglobulin levels before infusion on Day 1 of Cycle 1 and Day 22 of Cycles 1 to 3.

- If anti-HBc is positive: HBV-DNA as per assessment schedule. (Please see also Section 9.5.2.)
- Laboratory assessments from urine sampling before infusion (Day 1 preinfusion assessments will be considered baseline assessments):
 - Urinalysis on Day 1 of Cycles 1 to 3.
 - Urine pregnancy test in women of childbearing potential on Day 1 of Cycles 1 to 3.
- FcγRIIIa and FcγRIIa polymorphism (mucosal cheek swab) before infusion on Day 1, Cycle 1 (optional, see Section 10.9.7)
- 12-lead ECG on Day 1 of Cycle 1, and on Days 8 and 22 of Cycles 2 and 3

10.3 Follow-up Phase until Follow-up Visit 12

All patients who performed treatment Cycle 3 should have a follow-up visit 4 weeks after end of the last treatment cycle (4 weeks \pm 2 days after Cycle 3 Day 28). Patients should return for further follow-up visits until relapse of the lymphoma or for a maximum of 4 years. The second and third follow-up visit should be scheduled 6 weeks \pm 1 week following the previous visit, the fourth to sixth follow-up visit should be scheduled 3 months \pm 2 weeks following the previous visit, further follow-up visits should then be scheduled every 6 months. If not otherwise indicated, the following assessments should be performed at every follow-up visit:

- Patients with an ongoing response of at least PR after Cycle 3 may receive maintenance treatment with MOR00208 (12 mg/kg either every second week or monthly). Before administration, blood parameters (hematology, serum chemistry) should be evaluated in the local lab according to local guidelines/practice for the administration of monoclonal antibodies. A urine pregnancy test should be performed for women of childbearing potential. These lab results will only be captured in the eCRF if the administration visits coincide with the planned follow-up visits.
- Assessment of AEs and concomitant medication (see Section 9.8)
- Assessment of body weight
- Physical examination including palpable tumor assessment (general appearance, skin, head, eyes, ears, nose, throat, lungs, breasts and axillae (if applicable including bi-dimensional measurement of cervical, supraclavicular, axillary and inguinal lymph nodes), cardiovascular system, back and spine, abdomen (if applicable including spleen size below the costal margin), extremities, infusion site, lymph nodes, and neurological examination).
- ECOG performance status
- Vital signs (pulse, blood pressure, temperature and respiratory rate)

- Response assessment should be repeated at 2nd, 4th, 5th and all subsequent follow-up visits and include:
 - Assessment by physical examination
 - CT of neck, chest, abdomen and pelvis. A PET scan should also be used for response assessment if CT does not provide a clear readout and if the lymphoma is expected to be PET-avid. Follow-up radiographic evaluations may be performed any time \pm 4 days of the planned visit.
 - Radiological evaluation in addition to the CT/PET of neck, chest, abdomen and pelvis are to be done as appropriate (for MRI, please see Section 10.6). Radiological evaluations for response assessment should be performed at least for any procedure performed at baseline.
 - Bone marrow aspiration and biopsy (only to be repeated if previous response was not CR)
- Laboratory assessments from blood sampling:
 - Haematology including CBC with differential and platelet count and serum chemistry
 - Coagulation
 - PK sample at the 1st, 2nd and 3rd follow-up visit only
 - Anti-MOR00208 antibodies at the 1st and 3rd follow-up visit only
 - Serum immunoglobulin levels
 - β -HCG pregnancy test for women of childbearing potential (only urine pregnancy test is to be done if regular follow-up visit coincides with maintenance treatment visit; otherwise, serum pregnancy test should be done)
 - If anti-HBc is positive: HBV-DNA as per assessment schedule. (Please see also Section 9.5.2.)
- Laboratory assessments from urine sampling: Urinalysis

10.4 MOR00208 Treatment and Study Procedures after Follow-up Visit 12

Patients who have not progressed after four years of treatment with MOR00208 (ie, after Follow-up Visit 12 as described above) may continue receiving the IMP thereafter, until progression, based on the decision of the treating physician. The treatment frequency (during the follow-up period as described above) should be maintained.

Prior to each administration of MOR00208, the following assessments should be performed at a local laboratory:

- Assessment of body weight
- Haematology including CBC with differential and platelet count and serum chemistry

- β -HCG urine pregnancy test for women of childbearing potential (only urine pregnancy test is to be done if regular follow-up visit coincides with maintenance treatment visit; otherwise, serum pregnancy test should be done)
- Vital signs (pulse, systolic and diastolic blood pressure, body temperature, and respiratory rate) hourly
- Physical examination
- If anti-HBc was positive earlier: HBV-DNA should be measured every six months. (Please see also Section 9.5.2.)

Only the data on AEs, SAEs, and concomitant medications will be collected in the study database during this period.

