9.6 Management of Treatment-Related Toxicities

If a patient develops a study drug-related Grade 3 or 4 toxicity and the toxicity has not resolved to Grade 1 or to at least the baseline grade (if the condition was pre-existing at screening) at the day of the next scheduled administration, study drug administration for that visit will be postponed.

If treatment needs to be postponed for more than 15 days for the same study drug-related toxicity, the patient's treatment should be permanently discontinued. Patients who discontinue before end of Cycle 2 proceed with the EOS visit. Patients who have had at least SD at the end of Cycle 2 and have not progressed should continue with the first follow-up visit in the study (see [Section 9.10](#) and [10.3](#)).

If based on medical judgment, the treating physician considers a laboratory parameter change or adverse event not to be a study drug-related toxicity, but to represent natural fluctuation or progression of the underlying disease, it is up to the physician's discretion and assessment of the individual risk/benefit ratio to determine whether the patient should be dosed (see [Section 10.8.4](#)). The decision and rationale behind the decision should be documented in the source data.

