10.5 End of Study Visit

Patients will have their EOS 4 weeks (\pm 2 days) following:

- The last administration of MOR00208 in Cycle 2 if the response after 2 cycles was not at least SD
- The visit where a relapse (or disease progression) was diagnosed or decision to stop treatment was made in patients qualifying for Cycle 3 of MOR00208

If patient terminates the study early (ie, before end of Cycle 2), the EOS will be performed on the day of termination.

The assessments that will be performed at the EOS include the following:

- Assessment of AEs and concomitant medication
- Assessment of body weight
- Physical examination including palpable tumor assessment, general appearance, skin, head, eyes, ears, nose, throat, lungs, breasts and axillae (if applicable including bi-dimensional measurement of cervical, supraclavicular, axillary and inguinal lymph nodes), cardiovascular system, back and spine, abdomen (if applicable including spleen size below costal margin), extremities, infusion site, lymph nodes, and neurological examinations
- ECOG performance status
- Vital signs (pulse, blood pressure, temperature, respiratory rate)
- Response assessment includes:
 - Assessment by physical examination
- Laboratory assessments from blood sampling:
 - Haematology including CBC with differential and platelet count and serum chemistry
 - Coagulation

- B-, T- and NK cell flow cytometry
- Serum immunoglobulin levels
- β -HCG pregnancy test for women of childbearing potential
- Laboratory assessments from urine sampling: Urinalysis
- ECG

Patients who were positive for anti-HBc at screening should be followed up for potential HBV reactivation as per local practice (refer to [Section 9.5.2](#)).

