7.3.3 Immunogenicity

Patient has positive anti-MOR00208 antibodies (yes/no/missing) by visit:

- yes, if a titer is available
- no, if result is reported as negative
- missing, if anti-MOR00208 measurement is not available

Patient has developed positive anti-MOR00208 antibodies during study (yes/no/transient/not evaluable/missing):

- yes, if the patient has at least one positive post-baseline sample containing positive anti-MOR00208 antibodies including a positive result for the last sample analyzed; baseline sample has to be tested negative
- no, if baseline as well as all post-baseline results are negative
- transient, if the patient has at least one positive post-baseline sample containing positive anti-MOR00208 antibodies but a negative result for the last sample analyzed; baseline sample has to be tested negative
- not evaluable, if the baseline sample of the respective patient was tested positive
- missing, if no post-baseline anti-MOR00208 measurement is available

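### Patients who leave after Cycle 2 enter the anti-drug antibody rate on one post-baseline sample, taken at about day 29, because none is drawn at the end-of-study visit

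*Protocol*

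**What the plan says.** Immunogenicity is a secondary objective (Protocol 6.2), and the number and proportion of patients who develop anti-MOR00208 antibodies is a secondary endpoint (Protocol 7.3).

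**Sampling**
- Protocol 10.2, treatment phase: "Anti-MOR00208 antibodies before infusion on Day 1 of Cycles 1 to 3". The Cycle 3 sample is conditional: "assessments for Cycle 3 should only be performed if patient qualifies for the respective study drug administration".
- Protocol 10.3, follow-up: "Anti-MOR00208 antibodies at the 1st and 3rd follow-up visit only". The route into follow-up is Cycle 3: "All patients who performed treatment Cycle 3 should have a follow-up visit 4 weeks after end of the last treatment cycle".
- Protocol 9.6 has an exception for patients whose treatment is stopped for prolonged drug-related toxicity: "Patients who have had at least SD at the end of Cycle 2 and have not progressed should continue with the first follow-up visit in" (quote cut short). These patients therefore reach a visit with an antibody sample.
- Protocol 10.5: a patient without at least stable disease (SD) after two cycles has EOS four weeks after the last Cycle 2 infusion. A patient who terminates before the end of Cycle 2 has EOS on the day of termination. The list that begins "The assessments that will be performed at the EOS include the following" has blood tests for haematology and chemistry, coagulation, B-, T- and NK-cell flow cytometry, immunoglobulins and pregnancy. It has none for antibodies, and Table 2 has no EOS mark for them.
- Protocol 10.4: maintenance may continue beyond follow-up visit 12, with no antibody sample scheduled after follow-up visit 3.

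**Analysis**
- SAP 7.3.3 assigns the category *no* as follows: "no, if baseline as well as all post-baseline results are negative". It sets no minimum number or timing of samples. A patient with no post-baseline result is *missing*.
- SAP 11.7 takes as denominator every patient in the analysis group with at least one post-baseline assessment.

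**The concern.** A negative antibody status means only that no antibody was found while the patient was being sampled. Here the length of sampling depends on response. Patients who reach SD are sampled again at Cycle 3 and in follow-up. Patients who do not are last sampled halfway through their eight infusions. The SAP gives both groups the same *no* and the same weight in the rate.

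Two other groups are affected. Patients who leave before Cycle 2 Day 1 have no post-baseline sample and drop out of the rate as *missing*. Patients on maintenance may be dosed for years after their last scheduled sample.

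At stake is the estimate of a stated secondary endpoint. Because an antibody that appears after the last sample cannot be counted, the error from this source can only lower the reported incidence. It also makes antibody status hard to set against response, since the chance of detection itself differs by response.

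**Working it through.** The documents give no sample size, precision target or expected rate for immunogenicity, so there is no planned figure to reproduce. The check is a day count, followed by an illustration on stated assumptions.

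**1. Infusion days.** Protocol 10.2: "each 28-day cycle will consist of a MOR00208 infusion on Day 1, Day 8, Day 15 and Day 22 of the cycle". With Cycle 1 Day 1 as study day 1, Cycle 1 infusions fall on days 1, 8, 15 and 22. Cycle 2 infusions fall on days 28 + 1, 28 + 8, 28 + 15 and 28 + 22, that is days 29, 36, 43 and 50. These are nominal days: the visit window is ±1 day and postponement is allowed.

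**2. Patient below SD after Cycle 2.**
- Only post-baseline sample: predose at Cycle 2 Day 1, day 29.
- Time since the previous infusion: 29 − 22 = 7 days.
- Time from the sample to the last infusion: 50 − 29 = 21 days.
- EOS: 50 + 28 = day 78, which is 78 − 29 = 49 days after the sample.
- Infusions given after the sample: days 29, 36, 43 and 50, so 4 of 8.

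**3. Patient who enters Cycle 3 and stays in the study.**
- Cycle 3 Day 1 is two weeks after Cycle 2 Day 22: 50 + 14 = day 64.
- Cycle 3 Day 28: 64 + 27 = day 91.
- Follow-up visit 1: 91 + 28 = day 119.
- Follow-up visit 3, after two six-week intervals: 119 + 42 + 42 = day 203.

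| Path | Post-baseline antibody samples (about day) | Status if baseline and all samples are negative |
|---|---|---|
| Leaves before Cycle 2 Day 1 | none | *missing*, outside the rate |
| To EOS after Cycle 2, below SD | 29 | *no* |
| Cycle 3 and follow-up | 29, 64, 119, 203 | *no* |
| Maintenance after follow-up visit 3 | 29, 64, 119, 203; none later | *no* |

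**4. Possible size.** The inputs here are assumptions, not figures from the documents. Let p be the true incidence, L the share of evaluable patients who go to EOS after Cycle 2, and f the share of those patients' antibodies detectable by day 29. Assume the same p in all patients and full detection in the rest. Then

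reported rate = p × (L × f + 1 − L).

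- p = 5%, f = 0.5, L = 0.4: 5% × (0.20 + 0.60) = 4.0%.
- p = 5%, f = 0.5, L = 0.6: 5% × (0.30 + 0.40) = 3.5%.
- Wider range, most loss (L = 0.7, f = 0.25): 5% × (0.175 + 0.30) = 2.4%.
- Wider range, least loss (L = 0.3, f = 0.75): 5% × (0.225 + 0.70) = 4.6%.

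At the planned maximum of 120 patients, taking all as evaluable, the step from 5% to 3.5–4.0% is 120 × 1.0% = 1.2 to 120 × 1.5% = 1.8 patients.

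**5. With an EOS sample.** A patient leaving after Cycle 2 would have samples at about days 29 and 78. The second comes 28 days after the last infusion and follows all eight infusions instead of four.

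**The case against.** The strongest reply is about proportion. This is a Phase IIa study with no inference testing (Protocol 14.10), immunogenicity is descriptive, and no decision depends on it. On the assumptions above, the loss is one or two patients in 120. The exact 95% interval for 6 of 120 is 1.9–10.6%, so the shift lies well inside sampling error. SAP 7.3.3 also derives antibody status by visit, with a *missing* category, so a careful reader could see which visits contribute. All of this stands and limits the weight of the point. It does not remove it: the loss is systematic, runs in one direction and is tied to response, and the headline rate does not show it.

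A second reply is that a new EOS tube comes late. SAP 4.1 foresaw a cutoff in July 2015 by which all patients would have finished the main treatment period, while the current protocol is Amendment 5 of May 2020. On that timetable the tube recovers no one who left after Cycle 2. This also stands, and it is why a reporting remedy is needed as well.

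A reader might draw four stronger conclusions that the documents do not support:
- *That the SAP labels every such patient negative.* It does so only if baseline and all post-baseline results are negative. Positive, transient, not evaluable and missing each have their own category.
- *That a 5% incidence among the leavers would be reported as 2.5%.* The SAP plans no rate for that subgroup; rates are by subtype, for the combined indolent group and overall.
- *That circulating drug hides antibodies at day 29.* Neither the assay's drug tolerance nor a half-life value is given. Masking is possible but not shown, and nothing shows that an EOS sample would be free of it, especially when EOS falls on the day of early termination.
- *That everyone who stops treatment early is missed.* Under Section 9.6, patients with at least SD who stop for prolonged toxicity go to follow-up visit 1, which has a sample.

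**Conclusion.** The sampling gap and the classification rule are plain in the documents. Patients sent to EOS after Cycle 2 with a response below SD have one scheduled post-baseline antibody sample, at about day 29, with four of eight infusions still to come. If negative at baseline and on that sample, they count as antibody-negative on the same footing as patients sampled up to about day 203. Earlier leavers fall out of the rate, and maintenance patients are unsampled after follow-up visit 3.

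Reported incidence can therefore be biased low, more so in patients without disease control. By how much cannot be known from the documents. The 3.5–4.0% reading of a true 5%, and the wider 2.4–4.6%, rest wholly on the assumed incidence, share leaving and timing of onset. This is a cheap improvement to a secondary endpoint; it does not threaten the study's main conclusions.

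**What to change.** 1. **Protocol Section 10.5 and the EOS column of Table 2:** add one anti-MOR00208 serum sample (4 mL, as in Table 3) to the blood draw already made at EOS, for every patient still to reach EOS, including those on maintenance. SAP 7.3.3 and 11.7 already use any post-baseline result, so their definitions need no change for this sample.
2. **SAP 11.7:** for patients already past EOS, report antibody incidence by number and timing of post-baseline samples, at least Cycle 2 Day 1 only against later samples. Show the number classed as *missing* alongside.

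The cost is a protocol amendment, one extra tube and assay per remaining patient with no new visit, an SAP amendment and one extra table. The table serves all patients; the tube serves only those still in the study.
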